8.2.4 Change from Baseline

Change from baseline is calculated as:

- visit value at respective visit – baseline value.

Percentage change from baseline is calculated as:

- (change from baseline / baseline value) * 100.

If either the baseline or visit value is missing, the change from baseline and percentage change from baseline will be missing.

8.2.5 Multiple Assessments

All data will be reported according to the nominal visit date for which they were reported (that is, no visit windows will be applied during dataset creation and the visit will not be re-allocated if the actual visit date deviates from the planned date according to the visit schedule in the protocol). Unscheduled data will not be included in summaries but may

contribute to the End of Study (EOS) value, or best/worst case value (eg, shift tables) and will appear in listings.

If multiple laboratory samples for the same visit occur, it will be distinguished why this is the case. If an assessment was repeated due to technical problems the results from the valid measurement for this visit will be used in the analysis. If the measurement was repeated for safety reasons (ie, follow-up of abnormal lab values) or the reason for the repeated measurement cannot be ascertained, the initial measurement will be used.

Data from all assessments (scheduled and unscheduled), including multiple assessments, will be included in listings.

8.2.6 Actual and Planned Treatment

Both planned vial numbers integrated from the Interactive Response Technology (IRT) and the actual administered vial numbers will be collected via eCRF. If a subject's actual treatment is the same as the assigned treatment, then actual treatment is the assigned treatment.

The planned treatment for all subjects is 200 mg. Efficacy outputs will be displayed by planned treatment of 200 mg. For details on the derivation of efficacy variables see [Section 10.2.1](#).

The 400 mg loading dose for CSL312 naïve subjects is considered a single injection and a regular part of the planned 200 mg treatment regimen. AEs where the most recent dose was the loading dose will be flagged in listings of AEs.

In case of unexpected deviations from planned treatment including undefined dose modifications, overdoses and other deviations, an evaluation of that case and a final decision under what actual dose the subject should be presented for analysis will be done before DBL in the PARM.

8.3 Pre-defined Subgroups

The following subgroups are defined for the efficacy, safety, and/or PK/PD analyses. An overview table of which analyses are planned for specific subgroups is provided in [Table 5](#) (see [Section 17](#)).

8.3.1 CSL312-naïve and Non-CSL312-naïve Subpopulations

The following two subpopulations will be defined:

- CSL312-naïve subjects: subjects who were newly screened and enrolled for CSL312, without having taken part in a previous CSL312 study.
- Non-CSL312-naïve subjects: roll-over subjects from CSL312_2001 or CSL312_3001 who were part of a previous CSL 312 study. Subjects are included in this subpopulation regardless of which treatment they received in the previous study.

The subgroup analyses that will be conducted for those subpopulations are presented in [Table 5](#) (see [Section 17](#)).

8.3.2 Treatment-naïve and Non-treatment-naïve Subpopulations

The following two subpopulations will be defined:

- Treatment-naïve: Subjects who did not receive CSL312 before the start of this study, including CSL312-naïve subjects and rollover subjects who received only placebo in the CSL312_3001 study. There are no placebo subjects from CSL312_2001, so no subject rolling over from that study will be included in this subpopulation.
- Non-treatment-naïve: Rollover subjects who received CSL312 previously (ie, non-placebo subjects from CSL312_3001 and subjects from CSL312_2001).

In specific tables, the treatment-naïve subjects may be further differentiated into subjects with loading dose (newly enrolled for CSL312_3002) or without loading dose (rollover subjects previously receiving placebo).

The subgroup analyses that will be conducted for those subpopulations are presented in [Table 5](#) (see [Section 17](#)).

The main tables for QoL questionnaires WPAI:GH, TSQM II and AE-QoL will be presented stratified by treatment-naïve and non-treatment-naïve subjects (see [Sections 10.3.2.1](#) and [12](#) for further details). The time-to-event analysis (see [Section 10.3.1](#)) will be performed only for treatment-naïve subjects, with a further break-down of whether they received a loading dose. For these endpoints, this is considered the main analysis, not an additional subgroup analysis.

8.3.3 Previous Study and Treatment

The following three subpopulations will be defined:

- Roll-over subjects from CSL312_3001 who previously received Placebo.
- Roll-over subjects from CSL312_3001 who previously received CSL312.
- Roll-over subjects from CSL312_2001 who previously received CSL312.

The subgroup analyses that will be conducted for those subpopulations are presented in [Table 5](#) (see [Section 17](#)).

8.3.4 Japanese Subjects

Subjects will be counted as Japanese subjects if the respective site is in Japan and the race is entered as Asian in the eCRF. For the corresponding subgroup analyses, the following columns/groups will be presented:

- Japanese subjects.
- Non-Japanese subjects.
- Global study population (all subjects).

The subgroup analyses that will be conducted for those subpopulations are presented in [Table 5](#) (see [Section 17](#)).

8.3.5 Chinese and Asian Subjects

Asian subjects are all subjects with race “Asian” in the eCRF regardless where the site is located. Non-Asian subjects are all subject with race other than “Asian” in the eCRF. Asian subjects will be counted as Chinese subjects if the respective site is in Hong Kong or Taiwan. Chinese subjects will therefore be a subset of Asian subjects.

For the corresponding subgroup analyses, the following columns/groups will be presented:

- Asian subjects.
- Non-Asian subjects.
- Chinese Subjects.

The subgroup analyses that will be conducted for those subpopulations are presented in [Table 5](#) (see [Section 17](#)).

8.3.6 Adolescents

Adolescents are defined in this study as subjects with an age at date of informed consent (as entered into the eCRF on the Demographics page, information coming to the eCRF from IRT) ≤ 17 years.

For the corresponding subgroup analyses, the following columns/groups will be presented:

- Adults (> 17 years of age).
- Adolescents.

The subgroup analyses that will be conducted for those subpopulations are presented in [Table 5](#) (see [Section 17](#)).

Adolescents have additional PK/PD assessments at 3 days, 7 days, 14 days, 21 days, and 30 days after Visit Month 3. For details of the corresponding analyses, please see [Section 12](#) and [Section 13](#).

8.3.7 Pharmacokinetic Subgroup of Adult CSL312-naïve Subjects

There is a PK subgroup in a sub-set of adult CSL312-naïve subjects with additional PK/PD assessments to further characterize the PK of CSL312 following the SC loading dose. A target number of 12 CSL312-naïve adult subjects will be recruited from a subset of sites to be included in the subgroup. Additional analysis to be performed for this subgroup is described in [Section 12](#) and [Section 13](#).

8.4 Study Periods Relative to Treatment

AEs, HAE attacks, laboratory data, vital signs and other measurements will be assigned to the study time periods defined below.

Table 3 Definitions of Study Periods Relative to Treatment

Period	Start Date	End Date
Screening Period	Date of Informed Consent	Run-in Period Start Date
Run-in Period	Run-in Period Start Date	Day 1 Visit date of the Treatment Period or Date of Run-in Non-completion [whichever is first]
Treatment/Efficacy evaluation period	Date of Day 1 Visit of Treatment Period	Date of EOT Visit or EOS date [whichever is first]
Treatment/Efficacy before transition to AI evaluation period	Date of Day 1 Visit of Treatment Period	Date of first dose with AI – 1 Day (see Section 8.2.1)
Treatment/Efficacy after transition to AI evaluation period	Date of first dose with AI (see Section 8.2.1)	Date of EOT Visit or EOS date [whichever is first]
Follow-up	Date of EOT Visit	Date of Final/ Follow-up Visit
Safety evaluation period	Date and start time of First CSL312 Administration as entered in the eDiary	Date of Final/ Follow-up Visit
Safety Evaluation before transition to AI evaluation period	Date and start time of First CSL312 Administration as entered in the eDiary	Date of first dose with AI – 1 Day (see Section 8.2.1)
Safety Evaluation after transition to AI evaluation period	Date of first dose with AI (see Section 8.2.1)	Date of Final/ Follow-up Visit

The EOS date is the date entered in the Conclusion of Subject Participation eCRF page and should generally be identical to the date of the Follow-up Visit.

The handling of any unplanned dose changes or device changes will be discussed in the PARM. The safety evaluation period consists of the Treatment/Efficacy evaluation period plus the Follow-up Period.

Screening and Run-in periods will not be performed for roll-over subjects, instead relevant endpoint data (such as HAE attacks during the Run-in period) will be used from the CSL312_2001 and CSL312_3001 studies.

The duration of the Efficacy evaluation and the Safety evaluation period in days will be calculated as:

End Date – Start Date + 1 Day.

Screening, Run-in and Follow-up periods in days will be calculated as:

End Date – Start Date.

For CSL312-naïve subjects to assign events starting on Study Day 1 to the Run-in or Treatment/Efficacy evaluation period the start time of the event will be compared to the time of the first dose to determine if the event took place prior to the first dose (leading to assigning the event to Run-in) or after the first dose (leading to assigning the event to the Treatment/Efficacy or Safety evaluation period).

In the case that a non-CSL312-naïve (rollover) subject has an event recorded in this study that takes place prior to first treatment in this study, it will not be assigned to a period but still displayed in listings.

9 Study Population

Unless otherwise stated, all tables and listings in this section will be based on the Screened Analysis Set.

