3.1 Overall Design

This is a multicenter, open-label, phase 3b study designed to investigate long-term safety and efficacy of CSL312 when administered once monthly for at least 12 months. Subjects eligible to participate in this study may be:

- Subjects who participated in the phase 3 double-blind study CSL312_3001
- Subjects who participated in study CSL312_2001
- CSL312-naïve subjects with C1-INH HAE Type 1 / 2

The study consists of 4 periods: Screening, Run-in (for CSL312-naïve subjects), Open-label Treatment Period, and a Follow-up Period.

[figure not shown]
For subjects naïve to CSL312, there will be a Screening Period of up to 1 month followed by a Run-In Period, which may last at least 1 month and up to 2 months. CSL312-naïve subjects who meet all eligibility criteria during the Run-In Period will then enter the Treatment Period. Subjects who complete Studies CSL312_3001 and CSL312_2001 according to their respective protocols will be offered the opportunity to continue treatment by entering the CSL312_3002 Open-label Treatment Period. Subjects who reach the end of treatment or terminate the study early will have a follow-up telephone call 2 months after the End of Treatment Visit (End of Treatment Visit is 1 month after the last dose of CSL312). Subjects may switch to an HAE prophylaxis medication during the Follow-up Period.

Per Amendment 1, subjects or caregivers will subcutaneously administer CSL312 200 mg AI instead of CSL312 200 mg NSD. The AI is a device that contains the same prefilled syringe already being used in the NSD since the start of the study. The purpose of using an AI is to further facilitate the administration of CSL312. The dose and dosing regimen will continue to be 200 mg once monthly. Subjects who decline switching to CSL312 200 mg AI and who

have participated in the study for at least 12 months will receive 1 more dose of CSL312 200 mg NSD at the time of the scheduled site visit and subsequently proceed with the End of Treatment Visit 1 month later, as well as a Follow-up Visit 2 months after the End of Treatment Visit, as per the original protocol.

The study schematic is shown in Figure 1.

Figure 1 **CSL312_3002 Study Schematic**

EoT = End of Treatment; HAE = hereditary angioedema; OL = open-label.

^a The Follow-up Visit will be conducted via telephone call.

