4.3.4 Subjects Lost to Follow-up

If a subject repeatedly fails to return for scheduled visits, the site must attempt to contact the subject and counsel the subject on the importance of maintaining the assigned visit schedule and ascertain whether or not the subject wishes to and / or should continue in the study. All attempts to contact the subject should be documented in the subject's medical record.

A subject will be considered lost to follow-up if he or she repeatedly fails to return for scheduled visits and is unable to be contacted by the study site. Subjects lost to follow-up will be considered to have withdrawn from the study.

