10.3.2.1.2 Efficacy Secondary Endpoints

The secondary efficacy endpoints will be analyzed using the ATS Analysis Set. The endpoint “Time-normalized number of HAE attacks” will also be analyzed using the PP Analysis Set.

Subjects will enter HAE symptoms into their eDiary and the start and end date and time, the interference of HAE symptom(s) with daily activities, and location(s) of the HAE symptom(s). Investigator-reported HAE attacks will be based upon review of subject diaries, relevant interval medical history, and physician judgment. The investigator may ask clarifying questions to assist in his / her assessment of whether an HAE attack occurred. If an attack occurred, then the investigator will record an attack in the CRF, the start/end date, the attack location(s), and the severity of the attack based on the most severe symptoms.

For all analyses considering HAE attacks, only the HAE attacks confirmed and reported by the investigator will be used.

The time-normalized number (per month) of HAE attacks is calculated per subject as:

$$[\text{the number of HAE attacks} / \text{length of subject treatment in days}] * 30.4375$$

where the length of subject treatment is calculated as:

$$[\text{the date of End of Treatment Visit} - \text{the date of Study Visit Day 1} + 1]$$

The time-normalized number of HAE attacks per month will be summarized descriptively by 200 mg CSL312 once monthly overall, including median (primary) and mean (secondary)

with corresponding 95% CIs. The time-normalized number of HAE attacks will also be calculated for the Run-in Period. For non-naïve subjects, the Run-in Period of their previous CSL312 study will be used.

The secondary efficacy endpoint of the percentage reduction in the time-normalized number of HAE attacks is calculated within a subject as:

$$100 * [1 - (\text{time-normalized number of HAE attacks per month during treatment} / \text{time-normalized number of HAE attacks per month during Run-in})]$$

and will be summarized descriptively by 200 mg CSL312 once monthly overall. For non-naïve subjects, the Run-in Period of their previous CSL312 study will be used.

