10.2.1 Secondary Efficacy Analysis

The secondary efficacy endpoints will be analyzed using the ATS Analysis Set. The endpoint “Time-normalized number of HAE attacks” will also be analyzed using the PP Analysis Set. All efficacy analysis will not differentiate between treatment administration with NSD or AI and will be based on the overall Treatment/Efficacy evaluation period.

Subjects will enter HAE symptoms into their eDiary and the start and end date and time, the interference of HAE symptom(s) with daily activities, and location(s) of the HAE symptom(s). Investigator-reported HAE attacks will be based upon review of subject diaries, relevant interval medical history, and physician judgment. The investigator may ask clarifying questions to assist in his / her assessment of whether an HAE attack occurred. If an attack occurred, the investigator will record an attack in the eCRF, the start/end date, the attack location(s), and the severity of the attack based on the most severe symptoms.

For all analyses considering HAE attacks, only the HAE attacks confirmed and reported by the investigator using the eCRF ‘HAE Attacks’ form will be used.

For CSL312-naïve subjects, HAE attacks with a start date on or after the first day of the Run-in Period but prior to the date and time of the first study drug administration will be counted for the Run-in Period. For subjects from CSL312_2001 and CSL312_3001 the number of HAE attacks in the Run-in Period of the previous study will be used. The HAE attacks that occurred during the Run-in Period of the lead-in study will be imported from the final analysis datasets of the respective lead-in study.

HAE attacks with a start date and time after the first study drug administration through the EOT Visit will be counted for the Treatment Period and will be included in the analyses of efficacy.

HAE attacks will be listed, including start date/time, end date/time, time between start of the attack and end of the most recent preceding attack, anatomical locations, severity, most recent actual CSL312 dose (loading dose of 400 mg or the monthly 200 mg dose), injection device (NSD or AI), potential trigger, duration in days, period in which the HAE attack occurred and how many on-demand medications were taken per HAE attack.

The following derived endpoints based on HAE attacks will be presented together in a listing:

- Time-normalized number of HAE attacks (per month and per year),

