10.2.1.1 Time-normalized number of HAE attacks

The time-normalized number (per month) of HAE attacks is calculated per subject as:

$$\frac{\text{the number of HAE attacks}}{\text{length of subject treatment in days}} * 30.4375$$

where the length of subject treatment is calculated as the duration of the Treatment/Efficacy evaluation period described in [Section 8.4](#).

To transform the length of subject treatment which is calculated in days in years the number of days is divided by 365.25. Thus, time-normalized number of HAE attacks per year is calculated per subject as:

$$\frac{\text{the number of HAE attacks}}{\text{length of subject treatment in days}} * 365.25$$

The time-normalized number of HAE attacks will also be calculated for the Run-in Period. For non-CSL312-naïve subjects, the Run-in Period of their previous CSL312 study will be used.

The time-normalized number of HAE attacks per month and per year will be summarized descriptively including median (primary measure of interest) and mean (secondary measure of interest) with corresponding 95% CIs. The CIs for the mean will be based on the t-distribution while distribution-free CIs will be used for the median.

Besides the time-normalized number of HAE attacks, the total number of HAE attacks (ie, not time-normalized) will also be summarized.

10.2.1.2 The Reduction in the Attack Rate during the Treatment Period compared to the Run-in Period

The secondary efficacy endpoint of the percentage reduction in the time-normalized number of HAE attacks is calculated within a subject as:

$$100 * \left(1 - \frac{\text{time normalized number of HAE attacks per month during treatment}}{\text{time-normalized number of HAE attacks per month during Run-in}} \right)$$

and will be summarized descriptively. For non-CSL312-naïve subjects, the Run-in Period of their previous CSL312 study will be used.

The number and percentage of responders and non-responders will be presented combined with corresponding 95% CI. A subject is classified as a responder if the percentage reduction in HAE attacks under treatment compared to the Run-in Period is $\geq 50\%$. In addition, the number and percentage of subjects with percentage reductions of $\geq 70\%$ and $\geq 90\%$ will be presented with corresponding 95% CIs.

Furthermore, the number and percentage of subjects with a percentage reduction of 100%, ie, who are attack-free, will be presented and summarized with corresponding 95% CI.

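### For a subject without an End of Treatment Visit, the SAP runs the efficacy period to the end-of-study date with no last-dose limit, so off-drug or unobserved days can enter the attack-rate denominator while attack counting and censoring have no matching end date.

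*SAP*

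**What the plan says.** SAP 8.4, Table 3, starts the Treatment/Efficacy evaluation period on the Day 1 Visit date and ends it at "Date of EOT Visit or EOS date [whichever is first"; the row for the period after transition to the autoinjector has the same end. Duration is end minus start plus 1 day. The EOS date is the one on the eCRF page for conclusion of participation, and it "should generally be identical to the date of the Follow-up Visit".

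Other rules that depend on this period, or should agree with it:

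- **Rate denominator, SAP 10.2.1.1:** "where the length of subject treatment is calculated as the duration of the Treatment/Efficacy evaluation period".
- **Attack counting, SAP 10.2.1:** "HAE attacks with a start date and time after the first study drug administration through the EOT Visit will be counted for the Treatment Period". SAP 8.4 separately assigns HAE attacks to the Table 3 periods.
- **Time to event, SAP 10.3.1:** censoring is at the EOT Visit, with no alternative.
- **Attack-free days, SAP 10.2.2.2:** any date in the period without a recorded attack is attack-free.
- **Planned injections, SAP 10.6:** treatment-period duration divided by 30, rounded down.
- **Protocol 10.3.2.1.2:** the denominator runs from Day 1 to "the date of End of Treatment Visit" only. SAP Section 5 does not list the EOS fallback as a change.

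The protocol puts the EOT Visit 1 month after the last dose and the follow-up contact 2 months later. In that interval, "Subjects may switch to an HAE prophylaxis medication during the Follow-up Period" (Protocol 3.1). At withdrawal, an EOT assessment is attempted but not guaranteed (Protocol 4.3.3). Protocol 4.3.4 on loss: "A subject will be considered lost to follow-up if he or she repeatedly fails to return for scheduled visits" and cannot be contacted.

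**The concern.** The EOT Visit normally comes before the EOS date, so the fallback matters mainly when there is no EOT Visit. The denominator can then extend about 2 months past the planned end of treatment, into time when the subject is off CSL312, may be on another prophylaxis, or may not be observed. Under Amendment 1 the eDiary can be switched off on the date of early termination (Amendment 1 schedule, footnote N).

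For the same subject, the attack count and the censoring date refer to a visit that does not exist, while the general assignment rule in SAP 8.4 would count recorded attacks up to EOS. Two programmers could follow the SAP faithfully and obtain different rates.

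The outputs exposed are the time-normalized rates, percentage reduction, responder categories, 3-month windows, attack-free days, the 30-day efficacy exclusion and calculated compliance. Treating unobserved days as attack-free also sits badly with SAP 10.5, which says missing efficacy data are not imputed.

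**Working it through.** The plan states no figure to reproduce here. The check applies the SAP's formulas to a subject without an EOT Visit.

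**Inputs**

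- Rate per month = attacks / duration in days × 30.4375 (SAP 10.2.1.1).
- Planned EOT at last dose + 30 days. With dosing every 30 days from Day 1, duration to planned EOT is 30 × doses + 1: 361 days for 12 doses and 91 days for 3.
- Assumed tail to EOS: 61 days (2 months). With Amendment 1's −14 day follow-up window it is 61 − 14 = 47 days.
- SAP 10.6 duration is read as the Table 3 duration.

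**One on-treatment attack, none counted in the tail**

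| | To planned EOT | To EOS, 61-day tail | Change |
|---|---|---|---|
| 12 doses | 1/361 × 30.4375 = 0.0843 | 1/422 × 30.4375 = 0.0721 | 361/422 − 1 = −14.5% |
| 3 doses | 1/91 × 30.4375 = 0.334 | 1/152 × 30.4375 = 0.200 | 91/152 − 1 = −40.1% |

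With a 47-day tail the falls are 11.5% (361/408) and 34.1% (91/138).

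**Responder status.** Assume a run-in rate of 2 per month and 3 attacks over 3 doses. Over 91 days the reduction is 100 × [1 − (3/91 × 30.4375)/2] = 49.8%, a non-responder. Over 152 days it is 69.96%, a responder at the 50% threshold and just short of 70%.

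**Compliance.** 3 of 3 doses: floor(152/30) = 5, so 3/5 = 60%. 12 of 12 doses: floor(422/30) = 14, so 12/14 = 85.7%. The first is outside the 80-120% range in SAP 9.2 and could remove a fully dosed subject from the Per Protocol set.

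**Attacks in the tail counted under SAP 8.4 (12 doses).** One on-treatment attack plus two in the tail gives 3/422 × 30.4375 = 0.216 against 0.084. None on treatment plus one in the tail gives 0.072 against 0, and attack-free status is lost. The break-even number of tail attacks is k × 61/361 for k on-treatment attacks: 0.17 for k = 1 and 0.68 for k = 4.

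**EOS near the planned EOT.** If EOS equals planned EOT, nothing changes. If it falls 15 days earlier, there is no off-drug tail; the denominator is shorter and the 12-dose rate is 361/346 − 1 = 4.3% higher than at planned EOT for the same attack count.

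**Cohort mean.** Assume 1% to 10% of subjects lack an EOT Visit, rates are equal across subjects and no tail attack is counted. The change is fraction × (ratio − 1):

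- 12 doses, 61-day tail: −0.14% to −1.45%.
- 3 doses, 61-day tail: −0.40% to −4.01%.
- 3 doses, assumed 180-day tail (ratio 91/271): −0.66% to −6.64%.

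**The case against.** The strongest reply is that the tail may not exist. EOS is only generally the Follow-up Visit date. Follow-up is timed from the EOT Visit, so a subject without that visit has no anchored follow-up date. Protocol 4.3.2 has the investigator record the withdrawal date, and 4.3.4 treats lost subjects as withdrawn, so EOS may simply be the withdrawal date. This stands as a limit on size. It does not remove the defect, because the SAP does not say which date applies to these subjects and sets no last-dose limit.

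A reader might infer that the rule always favours the drug. The documents do not support that: attacks are still collected up to the follow-up contact, and SAP 8.4 could bring off-drug attacks into the count.

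A reader might also infer that a lost subject gains many months of attack-free time, because visits are 6 months apart after Month 12, or that treatment failures concentrate among such subjects. Neither is established. No passage fixes EOS that late, a missed site visit does not mean missing home diary data, and withdrawal may be administrative.

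Finally, the endpoints are secondary and descriptive, the median is the primary measure, EOT assessments are attempted at withdrawal, and the EOT and EOS dates are listed. These points stand and limit the importance of the issue.

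**Conclusion.** The end-date rule is faulty as written, and the SAP's own sections disagree for subjects without an EOT Visit. Their rates are understated where tail attacks are not ascertained or not counted, and can be overstated where off-drug attacks are counted. No off-drug tail enters if EOS falls no later than 1 month after the last dose.

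For one subject the effect can be material: a 14.5% to 40.1% lower rate in the illustrations, which rest on a 61-day tail with no tail attack counted. The number of affected subjects is not in the documents. If they are few, the cohort mean moves little; a subject with no counted attack keeps a zero rate whatever the denominator, so the median probably moves little too. Responder categories, attack-free days and Per Protocol membership are more exposed. This should be corrected, but it does not threaten the study's main conclusions.

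**What to change.** Keep the EOT Visit date as the end for every subject who has one, so that observed days are not discarded when the visit is late. For subjects without one, in the overall and after-autoinjector efficacy rows of Table 3, end the period at the earliest of:

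- the EOS date;
- last CSL312 dose + 34 days (the protocol's 1-month EOT interval, taken as 30 days, plus its 4-day visit window);
- the last documented site contact or visit at which HAE attacks were reviewed.

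Do not use the last eDiary symptom entry. Those entries are made when symptoms occur, so ending there would tie the denominator to the outcome.

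Use the same date for attack counting (10.2.1), the rate denominator, 3-month windows, attack-free days, time-to-event censoring (10.3.1) and planned injections (10.6). List the departure from the protocol formula in SAP Section 5.

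In the illustrations, if the 34-day limit is the earliest date, the durations become 331 + 34 = 365 and 61 + 34 = 95 days. The rates are 30.4375/365 = 0.083 and 30.4375/95 = 0.320. Planned injections return to 12 and 3, so compliance is 100%.

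The cost is one extra derivation, and some subjects' rates may become slightly less favourable.
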